14.2. Sample Size Justification

This study was designed and powered to show non-inferiority of the Test lens compared to the Control lens with respect to CLUE Comfort, logMAR Visual Acuity and Slit Lamp Findings (Grade 3 or higher). It was assumed there was no difference between the Test and Control lens with respect to CLUE comfort, visual performance and slit lamp findings.

In addition to the endpoints mentioned above this study was also powered to demonstrate the proportion of eyes with acceptable fitting on the Test lens is significantly superior to 90% as well as the cumulative odds ratio of (individual reduction items) the Test lens compared to the control lens is significantly superior to 1.00.

Unless otherwise specified, the sample size was calculated to achieve a minimum statistical power of 80% and a type I error of 5%.

The sample size calculation was based on historical data from a four similar randomized bilateral multi-site studies [REDACTED] where the same Test and Control lenses were used. Both lenses were worn as daily wear for at least 5 days per week for at least 6 hours per day. Follow-up visits occurred at 1 and 2-weeks after the initial visit. Subject accountability for each study is listed in Table 4 below.

[REDACTED]		
[REDACTED]	[REDACTED]	[REDACTED]

Table 6: Descriptive Summary of Slit Lamp Findings Pooled Across Historical Studies

%= nx100/N; SD=Standard Deviation

¹All SLF reported for this study are combined for the purposes of summarizing

² The percent (%) of Any Grade 2 is calculated using the Total Unique Eyes as the denominator

CLUE Comfort

Sample size calculation for CLUE comfort was carried out using an approximation of the power of an F-test derived from the non-centrality parameter calculated from the observed F statistic of a linear model⁸.

Model details:

CLUE comfort was analyzed using a linear mixed model. Lens type, period and the interaction between lens type and period were included in the model as fixed effects. A compound symmetric (CS) covariance was used to model the correlation between measurements on the same subject across study periods. Below is the variance-covariance matrix used in the CLUE Comfort model.

$$\sum_{comfort} \begin{pmatrix} 202 & 105 & 105 \\ 105 & 202 & 105 \\ 105 & 105 & 202 \end{pmatrix}$$

Visual Performance

The sample size calculation for distance monocular visual performance was performed assuming that there was no difference between the Test and Control lenses to achieve a minimum statistical power of 80%. Assuming a mean of 0 LogMAR, a standard deviation of 0.10 (based on historical ACUVUE® OASYS®) and a correlation between eye of 0.80, 2000 replicating trials were simulated for the repeated measurements from the multivariate normal distribution.

Acceptable Lens Fit

Acceptable lens fit is a binary response as y=1 if a subject eye has an acceptable fit and 0 otherwise. The common reference rate of 95% was selected for the sample size calculation, since this is considered to be a more conservative reference proportion. Assuming a correlation 0.80 between measurements within the same subject and period; and assuming a correlation of 0.50 between measurements within the same subject across periods. A total of 2000 replicating trials were simulated to estimate a sample size with a minimum statistical power of 80%.

Slit Lamp Findings

There was no Grade 3 or higher SLFs in any of the four historical studies. Therefore an incidence rate of 0.5% was chosen based on previous research literature^{3, 4}. Assuming a correlation 0.50 between measurements within the same subject and period; and assuming a correlation of 0.30 between measurements within the same subject across periods. A total of 2000 replicating trials were simulated to estimate a sample size with a minimum statistical power of 80%.

Table 7: Sample Size Estimates and Power Calculations for Primary Endpoints

Endpoint	Number per Subjects to Complete	Power
Distance Monocular Visual Acuity	40	>99%
SLFs Grade 3 or Higher	120	86%
Acceptable lens Fit	70	83%
CLUE Comfort	60	80%

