2.2. Endpoints

Primary Endpoints

The primary endpoints are as follows:

Biomicroscopy

Biomicroscopy will be assessed for each subject eye at all study visits (scheduled and unscheduled). The percentage of Grade 3 or higher slit lamp findings will be analyzed and will include corneal infiltrates.

Distance Monocular Contact Lens Visual Acuity

Distance monocular contact lens visual performance (logMAR) is assessed for each subject eye at the 2-week follow-up evaluation.

Fit Acceptance Rate

Acceptable lens fit will be assessed at all scheduled visits for each subject eye. Fit acceptance rate will be based on the lens fit acceptance of eyes wearing the Test lens only. Fit rates of the control lens will also be collected, but are not a primary endpoint.

CLUE Overall Comfort

Overall comfort scores are assessed using the Contact Lens User Experience (CLUE) questionnaire at the two-week follow-up. CLUE is a validated patient-reported outcomes questionnaire to assess patient-experience attributes of soft, disposable contact lenses (comfort, vision, handling, and packaging) in a contact-lens wearing population in the US, ages 18-65. Scores follow a normal distribution with a population average score of 60 (SD 20), where higher scores indicate a more favorable/positive response. (2016)¹.

Secondary Endpoints

The Secondary endpoints are as follows:

CLUE Overall Quality of Vision and Handling

Overall Quality of vision and handling scores are assessed using the Contact Lens User Experience (CLUE) questionnaire at the 2-week follow-up. CLUE is a validated patient-reported outcomes questionnaire to assess patient-experience attributes of soft, disposable contact lenses (comfort, vision, handling, and packaging) in a contact-lens wearing population in the US, ages 18-65. Scores follow a normal distribution with a population average score of 60 (SD 20), where higher scores indicate a more favorable/positive response (2016)¹.

Other Observations

Lens Preferences

Lens preferences will be assessed by patient reported outcome (PRO) questions regarding lens preference at the 2-week follow-up of the second wearing period. Subjects will be asked to choose for each preference item one of the following responses: Strongly Prefer the first lens, Prefer the first lens, no preference, prefer the second lens, strongly prefer the second lens. Lens preference questions consist of:

[REDACTED]

Driving Performance

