14.3. Analysis Populations

A separate Statistical Analysis Plan (SAP) will be provided for this study. If there are any discrepancies between the protocol and the SAP, the SAP will supersede the statistical sections in the protocol.

Safety Population:

All subjects who were administered any test article excluding subjects who drop out prior to administering any test article. At least one observation should be recorded.

Per-Protocol Population:

All subjects who have successfully completed all visits and did not substantially deviate from the protocol as determined by the trial cohort review committee prior to database hard lock (Per-Protocol Population). Justification of excluding subjects with protocol deviations in the per-protocol population set will be documented in a memo to file.

Intent-to-Treat (ITT) Population:

All randomized subjects regardless of actual treatment and subsequent withdrawal from study or deviation from protocol. At least one observation should be recorded.

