14.4. Level of Statistical Significance

The primary and secondary hypotheses will be tested with a type I error of 5% individually.

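### Table 7's power for lens fit (83% at 70) and slit lamp findings (86% at 120) does not follow from the stated inputs and success rules

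*Combined protocol and SAP*

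**What the plan says.** Section 14.2 sets the general target: "Unless otherwise specified, the sample size was calculated to achieve a minimum statistical power of 80% and a type I error of 5" percent. Section 14.4 repeats the level: "The primary and secondary hypotheses will be tested with a type I error of 5% individually". Neither says whether 5% is one-sided or two-sided. For fit and for SLF alike, Section 14.2 adds: "A total of 2000 replicating trials were simulated to estimate a sample size with a minimum statistical power of 80" percent.

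- **Fit inputs (14.2).** "The common reference rate of 95% was selected for the sample size calculation, since this is considered to be a more conservative reference proportion". The text continues "Assuming a correlation 0.80 between measurements within the same subject and period", with 0.50 across periods.
- **Fit data (2.2, 2.3, 5.1).** "Fit acceptance rate will be based on the lens fit acceptance of eyes wearing the Test lens only". All scheduled visits count. The sequences are Test/Control/Control and Control/Test/Test, so a subject has one or two Test periods.
- **Fit rule (14.5).** Success requires the lower limit of the two-sided 95% credible interval to exceed 0.90, that is, a posterior probability of at least 0.975.
- **SLF inputs (14.2).** The historical studies had no Grade 3 or higher findings. "Therefore an incidence rate of 0.5% was chosen based on previous research literature". No lens difference is assumed; the correlations are 0.50 within and 0.30 across periods.
- **SLF rule (14.5).** The upper limit of the two-sided 95% credible interval for Test minus Control, as proportions of eyes, must be below 0.05.
- **Table 7.** Visual acuity 40 subjects, CLUE comfort 60, fit 70 (83%), SLF 120 (86%). SLF therefore has the largest number, and it equals the completion target.

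**The concern.** Two eyes correlated at 0.80 add little to one eye, so 70 subjects carry far less information on fit than the number of assessments suggests, and 83% looks too high. In the other direction, a 5-point margin is very wide for an event with 0.5% incidence, so 86% at 120 looks too low.

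Section 2.3 requires every primary and secondary hypothesis to be met, so each power bears on the chance of overall success. Table 7 also tells the reader which endpoint sets the sample size. If both figures are off in these directions, it names the wrong one.

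**Working it through.** **Fit at 70: effective sample size, binary-scale correlations**

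Half the subjects (35) have one Test period and half have two.

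1. *One assessment per eye-period.* There are 35×2 + 35×4 = 210 observations. In units of p(1−p), the variance of a subject's sum is 2 + 2(0.80) = 3.6 for one Test period and 4 + 4(0.80) + 8(0.50) = 11.2 for two. Effective N = 210² / [35×(3.6 + 11.2)] = 44,100/518 = 85.
2. *All scheduled assessments.* Section 7.2 assesses fit three times in period 1 and twice in each of periods 2 and 3, giving 35×6 + 35×8 = 490 observations. With 0.80 for every pair within a subject and period, the variances are 6 + 30(0.80) = 30 and 8 + 24(0.80) + 32(0.50) = 43.2. Effective N = 490²/(35×73.2) = 94. Counting all visits changes little.
3. *Wald-type power* = Φ(0.05/SE − 1.96), with SE = √(0.95×0.05/N). For N = 85, SE = 0.0236 and power is 56%. For N = 94, SE = 0.0225 and power is 60%.
4. *Score-type power.* The critical proportion is 0.90 + 1.96√(0.09/N), that is 0.9637 or 0.9607. Power is 28% or 32%.
5. *What 83% would need.* Even by the Wald formula, N = 0.0475×[(1.96 + 0.954)/0.05]² = 161, against 85-94 available.

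**Fit: simulation**

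Correlated binary data, clustering respected, no discontinuation, 0.975 rule, one to three assessments per period:

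| Subjects | Binary-scale correlations | Latent-scale correlations |
|---|---|---|
| 70 | about 28-60% | about 44-76% |
| 120 | about 52-78% | about 70-90% |

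The upper ends are Wald intervals, whose type I error is about 5-8% against a nominal 2.5%. Logit intervals, with type I error near 2.5% at one assessment per period, give lower power: at 70, about 28-33% on the binary scale and 45-56% on the latent scale. A reduced Bayesian random-intercept model with the plan's priors gave 35-59% and about 44-52%. It omits the site, eye, period, sequence and carryover terms.

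At 120 the closed form gives effective N of 360²/888 = 146 or 840²/4,392 = 161, and a Wald power of 79% or 83%. The simulated Wald values are lower (72-78%) because the normal approximation is optimistic at a proportion this close to 1.

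**Attempts to reach 83% at 70**

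- One-sided 5% Wald bound, latent-scale correlations, all visits: about 81-83%, type I error about 9-10%.
- Ignoring clustering, two visits per period: 83.1-83.5%. At one visit this approach has type I error of about 10-13%.
- Reading p with the random effects at zero: about 100%, and 84-100% even when the true marginal rate is 90%.

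The first two reach 83% only by departing from the stated rule or inputs; the third overshoots it.

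**SLF at 120**

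Each lens contributes 60×2 + 60×4 = 360 eye-periods, so expected events are 720×0.005 = 3.6. The simulated SD of the difference is about 0.0055, which puts the margin 0.05/0.0055 = 9.1 SDs from zero.

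A cruder check treats the lenses as independent with only 120 observations each: SE = √(2×0.005×0.995/120) = 0.0091, and power = Φ(0.05/0.0091 − 1.96) = 99.98%. By the same formula, 86% needs 2×0.005×0.995×(1.96 + 1.080)²/0.05² = 37 per lens. Cluster-robust simulation and a reduced Bayesian random-intercept model give 99.97-100%.

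**The case against.** The strongest reply is that the simulation settings are not visible. Section 14.2 does not name the analysis inside the simulations, the correlation scale, the visits per period or the sidedness. The historical fit data are redacted. Section 14.3 adds: "If there are any discrepancies between the protocol and the SAP, the SAP will supersede the statistical sections in the protocol", and no separate SAP text stands in the combined document. This limits what can be said about how the figures arose. It does not restore them: no run that kept the stated correlations and the 0.975 rule, without discontinuation, exceeded 76% at 70.

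It is also fair that the trial targets 120 completers. With latent-scale correlations and all visits, fit at 120 reaches about 79-81% (logit) or 90% (Wald). On that reading the 80% minimum is roughly met; on the binary scale it is not.

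Four stronger readings are tempting but unsupported:

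- **That the fit-discontinuation rule shows 83% to be wrong.** Section 7.2 ends participation after an unacceptable fit with either lens. Depending on weighting and visits, applying this gives about 20-100% at 70. That range includes 83%, so it settles nothing.
- **That SLF power could be as low as 10-13%.** That figure comes from a fit without the baseline term and random effects that Section 14.5 requires, so it is not evidence about the planned analysis.
- **That the source of either figure is known.** The chance of at least one Grade 3 or higher event is about 86% on the binary scale, and ignoring clustering can give 83% for fit. Both matches are suggestive only. A subject-level, unpaired any-event comparison gives 60-89% for SLF, but the plan's unit is the eye.
- **That the trial is too small.** Section 14.2 calls 95% conservative, and a higher true fit rate would raise power.

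**Conclusion.** The point stands: two stated powers do not follow from the plan's own inputs and decision rules. Fit at 70 is about 28-60% or 44-76% by correlation scale, not 83%. At 120 it is about 52-78% or 70-90%, so the 80% minimum is not assured. SLF power at 120 is above 99% for an eye-level comparison, so 86% is understated. Table 7 therefore appears to have the limiting binary endpoint the wrong way round.

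This rests on a true fit rate of 95%, p read as the marginal proportion of eyes, equal allocation to the two sequences, no site effect, reduced Bayesian models, and SLF counted once per eye-period. Confidence is moderate. The failure to reproduce is consistent across methods, but the exact fit power depends on settings that the plan does not state.

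**What to change.** Rerun both simulations with the Section 14.5 models and the 0.975 rule, and state in Section 14.2:

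- the Test exposure per subject and all scheduled fit assessments;
- the scale of the correlations;
- p as the marginal proportion of eyes, and how it is derived from each model;
- how the existing fit-discontinuation rule (either lens) and replicates with no SLF events are handled.

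Restate the fit row at 70 and at 120 completers and the SLF row at 120, with whatever powers result. Align the 5% type I error in Sections 14.2 and 14.4 with the 0.975 rule. If the rerun confirms it, say that fit rather than SLF limits the sample size. A footnote giving the chance of no Grade 3 or higher event would help, because Section 14.5 falls back to Grade 2 when events are too few. If the separate SAP already holds these settings, cite it and correct Table 7 to match.

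The cost is two simulation runs, two table rows and some text. No extra subjects are proposed. The downside is that the stated fit power may become less favourable.

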14.3. Analysis Populations

A separate Statistical Analysis Plan (SAP) will be provided for this study. If there are any discrepancies between the protocol and the SAP, the SAP will supersede the statistical sections in the protocol.

Safety Population:

All subjects who were administered any test article excluding subjects who drop out prior to administering any test article. At least one observation should be recorded.

Per-Protocol Population:

All subjects who have successfully completed all visits and did not substantially deviate from the protocol as determined by the trial cohort review committee prior to database hard lock (Per-Protocol Population). Justification of excluding subjects with protocol deviations in the per-protocol population set will be documented in a memo to file.

Intent-to-Treat (ITT) Population:

All randomized subjects regardless of actual treatment and subsequent withdrawal from study or deviation from protocol. At least one observation should be recorded.

14.4. Level of Statistical Significance

The primary and secondary hypotheses will be tested with a type I error of 5% individually.

14.5. Primary Analysis

Primary efficacy analysis:

Visual Acuity

Distance monocular visual acuity (logMAR) will be analyzed using a Bayesian multivariate normal random-effects model to compare the Test and control lenses. The regression model will include sequence of lens wear, lens type and first-order carryover effect as fixed effects. Clinical site and subject nested within clinical site will be included as random effects. Other subject characteristics such as gender and age will be included as fixed effects when appropriate.

The Model:

Let $y_{ijklm} = (y_{1ijklm}, y_{2ijklm}, y_{3ijklm})$ denote the visual acuity (logMAR) for the m^{th} subject at the l^{th} site, assigned to the i^{th} lens for the j^{th} eye using the k^{th} sequence at periods 1, 2, 3, respectively. The likelihood for y_{ijkl} is constructed as follows:

$$y_{ijklm} \sim \mathcal{N}(\mu_{ijklm}, \Sigma)$$

Where $\mu_{ijklm} = (\mu 1_{ijklm}, \mu 2_{ijklm}, \mu 3_{ijklm})^T$ and Σ is a 3X3 variance-covariance matrix. Here,

$$\mu_{1ijklm} = \mu_0 + \pi_1 + \beta_1 \text{Lens}_{i[j,k]} + \beta_4 \text{Sequence}_k + \gamma_l + \delta_{l(m)} + \alpha_{j(m(l))}$$

$$\mu_{2ijklm} = \mu_0 + \pi_2 + \beta_2 \text{Lens}_{i[j,k]} - \beta_4 \text{Sequence}_k + \beta_5 \text{Carry1}_{i[j,k]} + \gamma_l + \delta_{l(m)} + \alpha_{j(m(l))}$$

$$\mu_{ijklm} = \mu_0 + \pi_3 + \beta_3 \text{Lens}_{i[j,k]} + \beta_4 \text{Sequence}_k - \beta_5 \text{Carry1}_{i[j,k]} + \gamma_l + \delta_{l(m)} + \alpha_{j(m(l))}$$

In this model π_1, π_2, π_3 represent the effect of period with the constraint $\pi_1 + \pi_2 + \pi_3 = 0$. In Lens I will be determined by the subject eye j and sequence k, therefore i is denoted as a function of j and k. We define $\text{Lens}_i=0$ for the control lens and $\text{Lens}_i=1$ for the Test lens, sequence is defined as: Sequence=0 for the order Control/Test/Test and Sequence=1 for order Test/Control/Control. The first-order carryover effect will be defined as carry=0 for the Control lens and carry=1 for the Test lens. So β_1 stands for the difference between the Test and control lens with respect to visual performance at period 1. A negative β_2 indicates the Test performed better than the control lens.

We assume random subject eye effects are independent and identically distributed (i.i.d) as $\alpha_{j(m(l))} \sim N(0, \sigma_{\text{eye/subject/site}}^2)$ as random eye nested within subject within clinical site, the random subject effect are i.i.d as $\delta_{l(m)} \sim (0, \sigma_{\text{subject/site}}^2)$ as random subject nested within clinical site and the random site effect is i.i.d as $\gamma_l \sim N(0, \sigma_{\text{site}}^2)$ for $i=1,2$ (lens), $j=1, 2$ (eye), $k=1, 2$ (sequence), $\text{carry1}=1, 2$ (first-order carryover effect) and $l=1 \dots |m_l(\text{subject/site})|$ and $l=1, 2, 3, 4$ and 5 (site).

For the β coefficients, independent non-informative priors $N(0, 1000)$ will be used. For the variance of random effects $\sigma_{\text{eye/subject/site}}^2$, $\sigma_{\text{subject/site}}^2$ and σ_{site}^2 independent non-informative conjugate priors inverse-gamma(0.001, 0.001) will be used. For Σ , non-informative conjugate priors inverse-wishart(3,S) will be used where S is a 3X3 variance-covariance matrix of y_{ijklm} . The metropolis sampler algorithm as implemented in the SAS/STAT MCMC procedure will be used to estimate the posterior distribution of the unknown parameters. Inferences will be made based on the 95% posterior credible intervals for relevant parameters.

Hypothesis Testing

The null and alternative hypothesis for visual acuity (logMAR) to test for non-inferiority of the Test lens relative to the control lens is as follows:

$$H_0: \frac{\beta_1 + \beta_2 + \beta_3}{3} \geq 0.05$$

$$H_A: \frac{\beta_1 + \beta_2 + \beta_3}{3} < 0.05$$

Non-inferiority will be declared if the upper limit of the 95% credible interval of the difference between the Test and Control is below 0.05, i.e. $P(\frac{\beta_1 + \beta_2 + \beta_3}{3} < 0.05) \geq 0.975$. Superiority will be established if the upper limit of the 95% credible interval of the difference between the Test and Control lens is below 0.0, i.e. $P(\frac{\beta_1 + \beta_2 + \beta_3}{3} < 0.0) \geq 0.975$. Superiority will be tested only if non-inferiority is met.

CLUE Overall Comfort

CLUE Comfort scores will be analyzed using a Bayesian multivariate normal random-effects model to compare the Test and control lenses. The regression model will include baseline CLUE comfort scores, sequence of lens wear, lens type and first-order carryover as fixed

effects. Clinical site will be included as random effects. Other subject characteristics such as age, gender, race and iris category will be included when appropriate.

The Model:

Let $y_{ijkl} = (y_{1ijkl}, y_{2ijkl}, y_{3ijkl})$ denote the CLUE Comfort score for the l^{th} subject at the k^{th} site, assigned to the i^{th} lens using the j^{th} sequence at periods 1, 2 and 3. The likelihood for y_{ijkl} is constructed as follows:

$$y_{ijkl} \sim \mathcal{N}(\mu_{ijk}, \Sigma)$$

Where $\mu_{ijkl} = (\mu_{1ijkl}, \mu_{2ijkl}, \mu_{3ijkl})^T$ and Σ is a 3X3 variance-covariance matrix. Here,

$$\mu_{1ijkl} = \mu_0 + \pi_1 + \beta_1 \text{Lens}_{[i,j]} + \beta_4 \text{baseline} + \beta_5 \text{Sequence}_j + \gamma_k$$

$$\mu 2_{ijkl} = \mu_0 + \pi_2 + \beta_2 \text{Lens}_{[i,j]} + \beta_4 \text{baseline} - \beta_5 \text{Sequence}_j + \beta_6 \text{Carry1}_{[i,j]} + \gamma_k$$

$$\mu_3{}_{ijkl} = \mu_0 + \pi_3 + \beta_3{}_{Lens[i,j]} + \beta_4{}_{baseline} + \beta_5{}_{Sequence[i]} - \beta_6{}_{Carry1[i,j]} + \gamma_k$$

In this model π_1, π_2, π_3 represent the effect of period with the constraint $\pi_1 + \pi_2 + \pi_3 = 0$. Lens I will be determined by sequence j, therefore i is denoted as a function of j. We define Lens=0 for the control lens and Lens = 1 for the Test lens, sequence is defined as: Sequence=0 for the order Control/Test/Test and Sequence=1 for order Test/Control/Control. The first-order carryover effect will be defined as carry=0 for the Control lens and carry=1 for the Test lens. So β_1 stands for the difference between the Test and Control lens with respect to CLUE comfort; A positive β_1 indicates the Test performed better than the control.

We assume random site effect is independent and identically distributed (i.i.d) as $\gamma_k \sim N(0, \sigma_{site}^2)$ for site for $i=1, 2$ (lens), $j=1, 2$, (sequence), $k=1, 2, 3, 4$ and 5 (site) .

For the β coefficients, independent non-informative priors $N(0, 1000)$ will be used. For the variance of random effect of σ_{site}^2 an independent non-informative conjugate prior, inverse-gamma(0.001, 0.001) will be used. For Σ , non-informative conjugate priors inverse-wishart(3,S) will be used where S is a 3X3 variance-covariance matrix of y_{ijkl} . Starting values for the mean and variance of CLUE scores will be 60 and 400 (since standard deviation of CLUE is normalized to be 20), respectively. The Metropolis sampler algorithm as implemented in the SAS/STAT MCMC procedure will be used to estimate the posterior distribution of the unknown parameters. Inferences will be made based on the 95% posterior credible intervals for relevant parameters.

Hypothesis Testing

The null and alternative hypotheses for CLUE comfort non-inferiority of the Test lens relative to the control lens are as follows:

$$H_o: \frac{\beta_1 + \beta_2 + \beta_3}{3} \leq -5$$

$$H_A: \frac{\beta_1 + \beta_2 + \beta_3}{3} > -5$$

Non-inferiority will be declared if the lower bound of the 2-sided 95% credible interval of the difference between the Test lens and the control lens is greater than -5, i.e., $P(\frac{\beta_1 + \beta_2 + \beta_3}{3} > -5) \geq 0.975$. Superiority will be declared if the lower bound of the 2-sided 95% credible interval of the difference between the Test and Control lens is greater than 0, i.e., $P(\frac{\beta_1 + \beta_2 + \beta_3}{3} > 0) \geq 0.975$. Superiority will only be tested if non-inferiority is established.

Lens Fit Acceptance

Lens fit acceptance will be analyzed using a Bayesian Logistic regression random-effects model to estimate the proportion of subjects eyes wearing the Test lens having acceptable lens fitting. The regression model will include period, sequence of lens wear and first order carryover effect. Site, subject nested within site and eye within subject within site will be included in the model as random effects.

Let $y_{ijklm}=1$ if an acceptable lens fit is observed for eyes wearing the Test lens only and $y_{ijklm}=0$ otherwise for the m^{th} subject, from the l^{th} site, for the i^{th} eye in the j^{th} period using the k^{th} sequence.

$$Y_{ijklm} \sim \text{Binary } (p_{ijklm})$$

$$p_{ijklm} = \frac{\exp(\text{Numerator})}{1 + \exp(\text{Numerator})}$$

$$\text{Numerator} = \beta_0 + \beta_1 \text{Lens}_{i[j,k]} + \beta_3 \text{period}_{j1} + \beta_4 \text{period}_{j2} + \beta_5 \text{sequence}_k + \beta_6 \text{Carry1}_{i[j,k]} + \gamma_1 + \delta_{m(l)} + \alpha_{j(m(l))}$$

We assume the random subject eye effects are i.i.d as $\alpha_{j(m(l))} \sim N(0, \sigma_{\text{eye/subject/site}}^2)$ for eye nested within subject within clinical site, the random effect for subject are i.i.d as $\delta_{m(l)} \sim N(0, \sigma_{\text{subject/site}}^2)$ for subject nested within clinical site and the random clinical site effects are i.i.d as $\gamma_m \sim N(0, \sigma_{\text{site}}^2)$ for $i=1, 2$ (eye), $j=1, 2, 3$ (period) $k=1, 2$ (Sequence) $l=1, \dots, 5$ (Site) $m=1, \dots, n_l$ (subject/site).

For the β coefficients, independent non-informative priors $N(0, 10000)$ will be used. For the variance of random effects of $\sigma_{\text{eye/subject/site}}^2$, $\sigma_{\text{subject/site}}^2$ and σ_{site}^2 , independent non-informative conjugate priors inverse-gamma (0.001, 0.001) will be used. The Metropolis-Hastings algorithm as implemented in the SAS/STAT 14.1 PROC MCMC procedure will be used to estimate posterior distributions of the unknown parameters. Inferences will be made based on the posterior credible interval for the relevant parameters.

Hypothesis Testing

With respect to Acceptable lens fit the null and alternative hypothesis for superiority is as follows:

$$\begin{aligned} H_0 &= p \leq 0.90 \\ H_1 &= p > 0.90 \end{aligned}$$

Where, p represents the proportion of subject eyes that achieve acceptable fit for the Test lens.

Success for acceptable fit will be declared if the lower bound of the 2-sided 95% credible interval of the proportion is greater than 0.90; i.e. $P(P > 0.90) \geq .975$.

Primary safety analysis:

Slit Lamp Findings

Grade 3 or higher slit lamp findings will be analyzed using a Bayesian Logistic regression random-effects model to compare the Test and Control lenses. The regression model will include baseline slit lamp findings, lens type, period, sequence of lens wear and first order carryover effect. Site, subject nested within site and eye within subject within site will be included in the model as random effects.

Let $y_{ijklmn}=1$ if a Grade 3 or higher SLF is observed and $y_{ijklmn}=0$ otherwise for the n^{th} subject, from the m^{th} site, assigned to the i^{th} study lens for the j^{th} eye in the k^{th} period using the l^{th} sequence.

$$Y_{ijklmn} \sim \text{Binary}(p_{ijklmn})$$

$$p_{ijklmn} = \frac{\exp(\text{Numerator})}{1 + \exp(\text{Numerator})}$$

$$\begin{aligned} \text{Numerator} = & \beta_0 + \beta_1 \text{Lens}_{ij[k,l]} + \beta_2 \text{Baseline SLF}_1 + \beta_3 \text{period}_{k1} + \beta_4 \text{period}_{k2} + \\ & \beta_5 \text{sequence}_k + \beta_6 \text{Carry1}_{i[k,l]} + \gamma_m + \delta_{n(m)} + \alpha_{j(n(m))} \end{aligned}$$

We assume the random subject eye effects are i.i.d as $\alpha_{j(n(m))} \sim N(0, \sigma_{\text{eye/subject/site}}^2)$ for eye nested within subject within clinical site, the random effect for subject are i.i.d as $\delta_{n(m)} \sim N(0, \sigma_{\text{subject/site}}^2)$ for subject nested within clinical site and the random clinical site effects are i.i.d as $\gamma_m \sim N(0, \sigma_{\text{site}}^2)$ for $i=1,2$ (lens), $j=1, 2$ (eye) , $k=1, 2, 3$ (period) $l=1, 2$ (Sequence) $m=1, \dots, 5$ (Site) $m=1, \dots, n_m$ (subject/site).

In this model, the lens I will be determined by the period k and sequence l , therefore i is denoted as a function of j and k . We define $\text{Lens}_i=0$ for the Control lens and $\text{Lens}_i=1$ for the Test lens.

For the β coefficients, independent non-informative priors $N(0, 10000)$ will be used. For the variance of random effects of $\sigma_{\text{eye/subject/site}}^2$, $\sigma_{\text{subject/site}}^2$ and σ_{site}^2 , independent non-informative conjugate priors inverse-gamma (0.001, 0.001) will be used. The Metropolis-Hastings algorithm as implemented in the SAS/STAT 14.1 PROC MCMC procedure will be used to estimate posterior distributions of the unknown parameters. Inferences will be made based on the posterior credible interval for the relevant parameters.

Hypothesis Testing

The null and alternative hypothesis for Non-inferiority is as follows:

$$H_0: p = (p_{\text{Test}} - p_{\text{Control}}) \geq 0.05$$

$$H_A: p = (p_{Test} - p_{Control}) < 0.05$$

Where p represents the difference between the proportion of subject's eyes with Grade 3 or higher SLFs of the test group compare to the control group. Non-inferiority will be established if the upper limit of the 2-sided 95% credible interval is below 0.05, i.e. $P(p=p_{Test} - p_{Control} < 0.05 | y)=0.975$.

In the event that the number of Grade 3 or higher SLFs is too small Grade 2 or higher SLFs will be analyzed and tested as described above.

